## 1. BACKGROUND

### 1.1 Cytokine Storm in COVID-19 and Hemophagocytic Lymphohistiocytosis (HLH)

Evidence is accumulating that patients with severe COVID-19 infection have a cytokine storm syndrome. Cytokine changes similar to secondary hemophagocytic lymphohistiocytosis (HLH) have been seen in COVID-19 and are associated with disease severity. The cytokines known to be elevated in HLH and COVID-19 are interleukin (IL)-2, IL-7, granulocyte colony stimulating factor, interferon- $\gamma$  inducible protein 10, monocyte chemoattractant protein 1, macrophage inflammatory protein 1- $\alpha$ , and tumor necrosis factor- $\alpha$ . A recent retrospective, multicenter study of 150 confirmed COVID-19 cases in Wuhan, China, demonstrated predictors of mortality which included elevated ferritin (mean 1297.6 ng/mL in non-survivors v. 614.0 ng/mL in survivors; p<0.001) and IL-6 (mean 11.4 ng/mL in non-survivors v. 6.8 in survivors; p<0.0001). This suggests that mortality in COVID-19 may be partially driven by virally associated hyperinflammation with resulting increase in markers of inflammation. Cytokine modulation with monoclonal antibodies such as tocilizumab (anti-IL-6) and anakinra (anti-IL-1) are being studied elsewhere in phase III trials and are being given on an ad hoc basis at Boston Medical Center. The safety and efficacy of these medications in COVID is unproven. The Infectious Disease Society of America (IDSA) recommends against treatment with biologic outside the context of a clinical trial. Treatment with etoposide will impact the cells elaborating multiple cytokines and may provide more robust reduction in inflammation. Etoposide has an established and predictable safety profile; its potential efficacy is supported by previous studies in HLH.

Hemophagocytic lymphohistiocytosis is a rare disorder of excessive immune activation with both laboratory and clinical evidence of severe inflammation. The etiologies of this syndrome include genetic mutations of cytotoxic function (familial HLH), as well as secondary causes such as infections, malignancy, or metabolic conditions (acquired HLH). HLH is well described in the pediatric population, but has also been described and studied in adult populations.

Hypercytokinemia mediates the clinical and laboratory presentation. Familial HLH typically presents in early childhood and is caused by mutations in genes important for NK and T-cell cytotoxic function. Secondary HLH is the phenotype that occurs in both children and adults in the absence of a known genetic cause. A retrospective study from the Mayo Clinic of 62 patients with secondary HLH revealed the cause to be a malignancy (52%), infection (34%), autoimmune disorder (8%), or unknown cause (6%). The most common malignancy observed was T cell lymphoma (59%) and the most common infection was Epstein Barr Virus (EBV) (26%).

HLH is diagnosed by a constellation of signs, symptoms, and laboratory abnormalities. Multiorgan dysfunction and critical illness are common. In 2004, The Histiocyte Society proposed an updated set of criteria to aid in identification of patients with HLH for clinical trials, which include molecular testing consistent with HLH or 5 of 8 of the following criteria: fever, splenomegaly, cytopenias affecting  $\geq 2$  lineages, hypertriglyceridemia and/or hypofibrinogenemia, hemophagocytosis (in bone marrow, spleen, or lymph node), hyperferritinemia, impaired NK cell function, and elevated soluble CD25 (sCD25) (ie, sIL2R). Other common findings include transaminitis, coagulopathy, hyponatremia, edema, rash, hypoalbuminemia, elevated lactate dehydrogenase (LDH), C-reactive protein, and d-dimer, and neurologic symptoms ranging from focal deficits to altered mental status. Elevated ferritin

occurs in the vast majority of patients with HLH but is nonspecific. The published criteria use a ferritin cutoff value of  $\geq 500$   $\mu\text{g/L}$  when diagnosing HLH. This is based on the HLH-94 study that showed a sensitivity of 84% at this level. Subsequent studies have demonstrated that a higher threshold of  $\geq 10,000$   $\mu\text{g/L}$  has a 90% sensitivity and 96% specificity for HLH. The diagnosis of secondary HLH can be challenging to make because the symptoms and laboratory features may overlap with other severe illnesses such as sepsis and hematologic malignancy, including disorders which are known to trigger HLH. Fardet *et al* created and validated the HScore, which includes 9 weighted variables based on a retrospective cohort of 312 patients. Some patients with cytokine storm from COVID-19 seen at Boston Medical Center meet formal HLH criteria, although bone marrow biopsies to confirm hemophagocytosis have not been routinely performed to make this assessment. Autopsies done on COVID patients at Boston Medical Center show evidence of hemophagocytosis in the lymph nodes and spleen, thereby suggesting that the true incidence of HLH in COVID patients is higher than pre-mortem estimates.

## **1.2 Etoposide Background and Proposed Mechanism of Action**

Etoposide has been used to successfully treat HLH. It inhibits topoisomerase II, which leads to double stranded DNA breaks. In a murine model of HLH, etoposide selectively depleted activated T cells leading to suppression of inflammatory cytokines and improved survival. Of note in this same study, dexamethasone had minimal benefit, despite the fact that dexamethasone is included in many clinical HLH regimens with the goal of further suppression of hypercytokinemia and inflammation. Etoposide may be more effective than cytokine-specific therapies because it eliminates the cells that are elaborating the cytokines, rather than targeting a specific cytokine in the evolving cytokine storm.

There are no prospective trials for treatment of HLH in adults, and treatment is largely based on the HLH-94 study, a large prospective pediatric study in patients less than 16 years old without history of immunosuppression or malignancy. In that study, the investigators used a regimen that included an 8 week induction with dexamethasone and etoposide. Response to treatment was determined by clinical and laboratory evidence of resolution, including fever curve, trend of sIL2R, LFTs, fibrinogen and ferritin level. Timely diagnosis and early administration of therapy has been demonstrated to improve survival. In a retrospective multicenter study of 162 patients with HLH looking at predictors of mortality, use of etoposide was associated with better survival.

Etoposide is an already FDA approved drug that is comparably inexpensive and currently available. Etoposide has an established safety profile and its use is supported by previous studies in HLH. We propose a Phase II study of etoposide for the treatment of cytokine storm in severe COVID-19 infection.

## **1.3 Rationale for Etoposide Clinical Study**

The cytokine storm related to COVID-19 appears to be similar to the hyperinflammation seen in other virally triggered secondary HLH. Others have postulated that the combination of topoisomerase I and topoisomerase II inhibitors could potentially be an effective treatment to

protect COVID 19 patients from cytokine storms. We posit that the cytokine storm seen in COVID-19 infection resembles secondary HLH seen as a result of other viral infections, resulting in an aberrant and overly exuberant cytokine response which is deleterious and leads to multiorgan dysfunction.

The rationale for the use of etoposide to treat the cytokine storm in COVID-19 is the high mortality associated with the hyperinflammatory response to the virus, which is similar to that seen in secondary types of HLH. Early use of etoposide has been shown to improve survival in secondary HLH. Autopsy studies of ARDS in COVID patients show a high number of cytolytic T cells in the lungs of such patients. Early autopsy results of COVID patients at BMC demonstrate significant hemophagocytosis in lymph nodes and spleen. Comparable studies in the related coronavirus infection SARS have demonstrated hemophagocytosis, a hallmark of HLH. By targeting the T cells and monocytes driving the cytokine storm in patients with the more severe forms of COVID infection, we hope to alleviate the progression of lung and multi-organ dysfunction characteristic of patients who die from this illness.

Potential concerns about the use of etoposide and dexamethasone for COVID-19 infected patients include decreased immune response and pathogen clearance. Studies in humans and animals indicate that corticosteroid immunosuppression (both inhaled and systemic) impairs induction of anti-viral type-I interferon responses to a range of respiratory viruses. Opinions on the use of steroids in COVID-19 are mixed, and based on limited data. A retrospective cohort study of 201 patients with confirmed COVID-19 pneumonia in Wuhan China, suggested that risk factors associated with the development of ARDS and progression from ARDS to death included older age, and neutrophilia, as well as organ and coagulation dysfunction (eg, higher lactate dehydrogenase [HR, 1.61; 95% CI, 1.44-1.79; and HR, 1.30; 95% CI, 1.11-1.52, respectively] and D-dimer [HR, 1.03; 95% CI, 1.01-1.04; and HR, 1.02; 95% CI, 1.01-1.04, respectively]). Among patients with ARDS, treatment with methylprednisolone decreased the risk of death (HR, 0.38; 95% CI, 0.20-0.72). The CDC cautions interpretation of this data given its observational by nature, and patients with MERS-CoV or influenza who were given corticosteroids were more likely to have prolonged viral replication, receive mechanical ventilation, and have higher mortality. Given the data in MERS and influenza, and the lack of randomized data demonstrating benefit of corticosteroids, others caution against the use of steroids in COVID 19 patients. For these reasons in the study proposed here, we do not plan to use corticosteroids as part of the treatment protocol.

Another potential concern is that decrease in cytotoxic T cell and humoral immune response with the administration of cytotoxic chemotherapy. Prolonged etoposide therapy has been shown to reduce cytotoxic T cell activity, macrophage/monocyte number and function, and humoral responses in animal models, some of which initiate low dose daily etoposide **prior to** a viral challenge. In HLH, etoposide has been argued to be effective as a result of its ability to ablate activated T cells. In the study proposed here, etoposide will be used well after patients have developed an established COVID infection and we plan to use a very limited dose and schedule of this drug so as to minimize the likelihood of arresting the production of neutralizing antibodies to COVID-19, but still allow ablation of cytolytic T cells that are leading to cytokine activation. To our knowledge, no studies have examined the immunologic effect of brief etoposide therapy relatively late in a human viral infection. Etoposide is used in the treatment of

HLH associated with Epstein Barr Virus (EBV) infection without known worsening of viral infection. In studies of hematologic malignancy patients who were inoculated with a varicella zoster vaccine, then underwent high dose chemotherapy followed by autologous stem cell transplant, neutralizing antibody production was detected despite this myeloablative regimen.

#### **1.4 Rationale for Dose Selection**

In this trial, patients will be treated with a markedly abbreviated course of the dosing regimen used in the current standard adult HLH protocol. In the standard HLH regimen, etoposide is given at 150 mg/m^2 twice a week for two weeks, followed by weekly therapy, in combination with dexamethasone. In this trial, patients will receive the standard initial two doses of etoposide in the first week (150 mg/m^2 IV x 2) on day 1 and 4 of treatment. Further etoposide therapy will not be given unless the assessment of the patient's subsequent course is that they improved after etoposide treatment but then had recurrent clinical deterioration, at which point further etoposide therapy would be allowed (according to the HLH-94 protocol) after discussion with the investigator.

The rationale for such an abbreviated course of etoposide is three fold. First, the immune hyperactivation in COVID infections may differ from that of patients with classic secondary HLH and may require only a relatively brief period of pharmacologic down-regulation. Second, the development of neutralizing antibodies to COVID are likely to be an important aspect of recovery from this illness and prolonged treatment with etoposide could theoretically blunt such a response. Third, prolonged etoposide therapy will induce more significant myelosuppression in a group of patients who will be susceptible to bacterial super-infection. The proposed two doses of IV etoposide is not expected to cause deep or prolonged myelosuppression.

### **2. STUDY PLAN**

#### **2.1 Study Design**

This is a randomized, open-label phase II study designed to evaluate the safety and efficacy of etoposide in patients with COVID-19 infection. Treatment will be comprised of etoposide administered intravenously at a dose of 150 mg/m^2 on Days 1 and 4 in patients with COVID-19 infection meeting eligibility criteria. Subsequent doses of etoposide will be allowed if the investigator and treating physician believe the patient had clinical benefit from etoposide therapy but subsequently has evidence of recurrent clinical deterioration.

Two cohorts of patients will be treated with etoposide. Cohort 1 will be patients who require intubation due to their severe COVID-19 related respiratory illness. Cohort 2 will be COVID-19 patients who have progressive pulmonary dysfunction and evidence of severe inflammation but who are not yet intubated. Although prior treatment for COVID with anti-cytokine therapy will not exclude a patient from enrollment on this trial, a “washout” period of at least 3 half-lives will be required prior to initiation of etoposide therapy. Enrollment will begin with cohort 1, following which a decision will be made to open cohort 2 or not, as outlined further in this document.

## **2.2 Number of sites**

One (Boston Medical Center, [name])

## **2.3 Number of patients**

- 32 patients in each cohort with 3:1 allocation ratio (24 etoposide and 8 control per cohort)
- 64 patients total

## **2.4 Primary Objective**

- Improvement in pulmonary status by two-categories on 8 point ordinal scale of respiratory function (See Section 8.2)

## **2.5 Secondary Objectives**

- Overall Survival at 30 days is a key secondary endpoint.
- Improvement in inflammatory markers associated with cytokine storm (Ferritin, C-Reactive Protein (CRP), d-dimer, white blood cell count)
- Cumulative incidence of grade 3 and 4 adverse events during hospitalization
- Cumulative incidence of serious adverse events during hospitalization
- Duration of hospitalization
- Duration of ventilation
- Ventilator free days (reintubations or death within 28 days will result in zero ascribed time off ventilator prior to reintubation)
- Improvement in oxygenation or paO2/FIO2 ratio

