### **3.2 Inclusion Criteria (applicable for patients enrolled for treatment or data collection)**

- Age 18 years or older
- Confirmed COVID-19 infection
- Evidence of cytokine storm defined as:
  - Peak ferritin > 10,000 ng/mL OR
  - Peak ferritin > 500 ng/mL and one or more of the following at any time during hospital admission:
    - Lactate dehydrogenase > 500 U/L, d-dimer > 1000 ng/mL, C-reactive protein > 100 mg/L, or WBC > 15 k/uL
- Cohort 1: Intubated status as a result of COVID infection-associated respiratory illness
- Cohort 2 (if activated): Evidence of progressive respiratory failure (requiring >4 L/min of supplemental oxygen to maintain SaO2 greater than 92%) without intubation

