## **5.3 Etoposide Administration**

Etoposide 150 mg/m^2 will be administered over 60 minutes intravenously on Days 1 and 4. Admixed in NS-500ml.

If the treating clinicians feel that the patient initially benefited from etoposide but then has evidence of relapse of cytokine storm, the patient may continue on the standard HLH etoposide schedule of day 8, 11, 18, 25 after discussion with one of the study investigators.

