## **5.4 Etoposide Expected Toxicities and Management**

Reversible myelotoxicity has been uniformly observed to be the major toxicity for VP-16 and to represent the only clinically significant side effect. Following a single IV injection, peak myelotoxicity occurs at seven to nine days. Following daily injections for five to seven days, myelotoxicity is maximal between 12-16 days from the initiation of therapy. Bone marrow suppression is mainly manifested as granulocytopenia, with thrombocytopenia and anemia occurring to a lesser extent. Gastrointestinal toxicities including transient modest nausea, vomiting, and diarrhea, are common. Other reactions could include aftertaste, rash, pigmentation, pruritis, abdominal pain, constipation, and dysphagia. Occasional alopecia is reported. VP-16 does not produce phlebitis or nephrotoxicity. Rarely anaphylactic-like reactions have been reported, as well as, hypotension. The drug is to be infused over 60 minutes in this study to decrease the potential for hypotension, and the blood pressure and pulse will be monitored during the infusion. Occasionally, chills, fever, peripheral neurotoxicity, stomatitis, hepatotoxicity, transient cortical blindness and radiation recall dermatitis may be a result of VP-16 administration. Stomatitis is usually associated with high dose regimens containing etoposide. The occurrence of acute leukemia has been reported rarely in patients treated with VP-16 in association with other antineoplastic agents. Etoposide can cause fetal harm when administered to a pregnant women. It has been shown to be teratogenic in mice and rats. In females of reproductive potential, etoposide may cause infertility and result in amenorrhea. Premature menopause can occur with etoposide. Recovery of menses and ovulation is related to

age at treatment. Males In male patients, etoposide may result in oligospermia, azoospermia, and permanent loss of fertility. Sperm counts have been reported to return to normal levels in some men, and in some cases, have occurred several years after the end of therapy Secondary leukemias associated with etoposide have been reported. Women of childbearing potential will be advised to avoid becoming pregnant for at least 6 months after the final dose of etoposide. Males with female partners of reproductive potential will be advised to use effective contraception for 4 months after the final etoposide dose.

Safety of etoposide for use by nursing women has not been established.

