## 7.2 Statistical Analysis

Tabulations overall, and by treatment group, will be produced for appropriate demographic, baseline, efficacy, and safety parameters, with number and percentages reported for categorical variables and the mean, median, standard deviation, and range for continuous variables. All analyses will be performed at an  $\alpha=0.05$  level using SAS v.4.

Efficacy analyses will be performed in an intention-to-treat (ITT) population consisting of all patients randomized. The difference in ordinal scale improvement rates between treatment arms will be calculated with a 95% confidence interval and formally compared using Fisher's Exact Test. For secondary analysis of the primary endpoint, logistic models individually adjusted for age, diabetes, chronic lung disease/moderate or severe asthma, immunocompromise, liver disease, heart disease/hypertension, smoking and obesity (BMI  $> 40$ ), residence in long-term care facility, will also be examined with odds ratios and 95% confidence intervals reported.

The analysis of secondary time to event endpoints including survival at 30 days, duration of hospitalization, duration of ventilation and ventilator free days, will be compared between treatment arms based on a log-rank test. The median will be estimated with a 95% CI for each treatment arm using the Kaplan-Meier method. Cox proportional Hazards models adjusted individually for age, diabetes, chronic lung disease/moderate or severe asthma, immunocompromise, liver disease, heart disease/hypertension, smoking and obesity (BMI  $> 40$ ), residence in long-term care facility, will also be examined with odds ratios and 95% confidence intervals reported. Changes in inflammatory markers and in oxygenation or  $\text{paO}_2/\text{FIO}_2$  ratio, based on available recorded measurements, will be compared between treatment arms using a two sample t-test, or a Wilcoxon Rank Sum test, as appropriate. Incidence of grade 3 or 4 AEs and serious AEs will be compared using Fisher's Exact test.

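### White blood cell count is listed as an efficacy marker, but etoposide's main stated toxicity also lowers it, so a difference between arms can reflect marrow suppression

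*Combined protocol and SAP*

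**What the plan says.** Section 2.5 of the combined protocol and SAP has this secondary objective: "Improvement in inflammatory markers associated with cytokine storm (Ferritin, C-Reactive Protein (CRP), d-dimer, white blood cell count". No direction is given for any marker. Section 7.2 says that changes in the markers, on whatever measurements are recorded, "will be compared between treatment arms using a two sample t-test, or a Wilcoxon Rank Sum test, as appropriate". It sets no analysis day and has no rule for low counts.

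Section 3.2 gives the laboratory signs which, with ferritin above 500 ng/mL, count as cytokine storm: "Lactate dehydrogenase > 500 U/L, d-dimer > 1000 ng/mL, C-reactive protein > 100 mg/L, or WBC > 15 k/uL".

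On the drug, section 5.4 says "Reversible myelotoxicity has been uniformly observed to be the major toxicity for VP-16". On form and timing it adds "Bone marrow suppression is mainly manifested as granulocytopenia, with thrombocytopenia and anemia occurring to a lesser extent" and "Following a single IV injection, peak myelotoxicity occurs at seven to nine days". Section 5.3 says that etoposide "will be administered over 60 minutes intravenously on Days 1 and 4". Under section 4.1 the controls receive standard of care without placebo.

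The section 6 calendar schedules a blood count with differential at screening, Days 1, 4 and 7, before discharge and at Day 30. A footnote adds counts at least twice weekly in hospital. Section 1.4 expects the marrow suppression from two doses to be neither deep nor long-lasting.

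**The concern.** An efficacy marker should move because the disease improves. This one also moves because of the drug's main toxicity, and only in the arm that receives the drug. Randomization does not help, since the assigned treatment itself causes the effect.

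The plan does not separate the two causes. It sets no lower bound on a favourable WBC, does not say how leukopenia or neutropenia is handled, and does not say that the differential will be used. The entry rule adds to the difficulty. WBC above 15 k/uL is only one of several qualifying signs and may have been met at any time in the admission. Some patients can therefore start treatment with an unremarkable count, and in them a fall is not evidence of recovery.

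At stake is the reading of one secondary result. A significant WBC difference could be reported as control of cytokine storm when it shows marrow suppression. The same fall could also appear as a grade 3 or 4 adverse event, and so count for efficacy and against safety.

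**Working it through.** **Direction.** Section 2.5 does not say that improvement in WBC means a fall. Section 3.2 treats a high count as a sign of cytokine storm, so a fall is the natural reading. This is an inference.

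**Timing.** Apply the 7-9 day peak in 5.4 to each dose separately:
- Day 1 dose: 1 + 7 = Day 8 to 1 + 9 = Day 10.
- Day 4 dose: 4 + 7 = Day 11 to 4 + 9 = Day 13.

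This is an approximation, because 5.4 gives the interval for a single injection and the trial gives two. Against these windows:
- Day 1 and Day 4 draws: taken before that day's dose, so before either peak.
- Day 7 draw: six days after the first dose and three after the second, one day before the earliest peak.
- Twice-weekly inpatient counts: can fall on Days 8-13.
- Pre-discharge count: inside the window only if discharge falls there; the documents give no discharge timing.
- Day 30: well past both windows, unless the optional doses on Days 8, 11, 18 and 25 (sections 4.4 and 5.3) are given.

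Since 7.2 fixes no day, counts from inside the window can enter the comparison.

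**Size, for illustration.** The plan gives no figure for this comparison: no expected fall, no SD of change and no power. Assume no anti-inflammatory effect at all, complete data in one cohort (24 v 8, section 2.3), normal changes with equal SD, and a toxic fall of *d* SDs relative to control.
- Degrees of freedom: 24 + 8 - 2 = 30.
- Noncentrality: *d* / sqrt(1/24 + 1/8) = *d* / sqrt(4/24) = *d* / 0.408 = 2.449 *d*.
- Chance of a significant result in etoposide's favour: the probability that a noncentral t on 30 degrees of freedom exceeds the 97.5% point of the central t.

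| Toxic fall *d* (SD) | Noncentrality | Chance of a significant improvement |
|---|---|---|
| 0 | 0 | 2.5% |
| 0.25 | 0.612 | 8.6% |
| 0.5 | 1.225 | 21.9% |
| 1 | 2.449 | 65.9% |

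In absolute units these shifts depend on the unknown SD. With an assumed SD of 5 k/uL they are falls of 1.25, 2.5 and 5 k/uL; with 10 k/uL they are 2.5, 5 and 10 k/uL. The figures are for the t-test. The Wilcoxon test would compare the same confounded changes.

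**The case against.** The best defence has four parts.

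**The fall may be small.** Section 1.4 expects suppression to be neither deep nor prolonged, and section 5.5 modifies or holds doses for several laboratory abnormalities. A reader might infer from 5.4 that WBC will fall enough to look like benefit. The documents do not support that; they support only that it can. Equally, an expectation that suppression will not be deep does not exclude a moderate fall.

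**The overlap in time is partial.** A reader might place the Day 7 count at the nadir, or assume that many pre-discharge counts lie there. By the plan's own interval, Day 7 comes just before the first peak, and discharge timing is not given. What remains is the twice-weekly counts and the absence of an analysis day.

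**The effects could be told apart.** The differential is collected, so neutrophils and lymphocytes can be read separately. Section 1.2 also gives depletion of activated T cells as the intended mechanism, so some fall in white cells could be a wanted effect. Both points are fair, but the objective names the total count, which cannot separate a wanted from an unwanted fall, and 7.2 does not commit to using the differential.

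**Little hangs on it.** Adverse events are compared separately, so a reader may see cytopenia beside the WBC result. That helps interpretation but leaves the fall in the efficacy test. The limited scope is conceded.

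Two further inferences also fail. One is that a neutropenic patient is the best responder: no WBC responder is defined, and improvement could mean return to normal. The other is that leaving LDH out of 2.5 is an error: it is a choice, and the confounding does not depend on it.

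**Conclusion.** The concern holds in limited form. As written, the plan can count marrow suppression as improvement in an inflammatory marker, and nothing in it distinguishes the two. This follows from the protocol's own text plus one inference, that improvement in WBC means a fall.

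The size cannot be fixed from the documents. The 9%, 22% and 66% rest on assumed shifts of 0.25, 0.5 and 1 SD and show how sensitive the comparison is; they do not predict its result. The affected item is one of four markers in one secondary objective. Ferritin, CRP, d-dimer, the primary respiratory endpoint, 30-day survival and the stopping rule in 9.5 are not touched. A reader might take the point as undermining the trial's efficacy case as a whole, and it does not. It should be corrected because the ambiguity is foreseeable and cheap to remove.

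**What to change.** - In 2.5, remove white blood cell count from the inflammatory markers.
- In 7.2, state that the marker comparison covers ferritin, CRP and d-dimer. The section names no individual marker at present.
- Report WBC, absolute neutrophil count and platelets by arm as safety laboratory data. Section 7.2 limits safety analyses to patients who took study treatment, so say explicitly that the control patients' counts are tabulated too.

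The cost is the loss of one secondary efficacy marker and a few lines of wording. No test, visit or patient is added, because the counts are already scheduled. LDH is drawn at every calendar visit and could be added as a fourth marker, but that is optional and not needed to cure the problem.

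If the sponsor prefers to keep WBC among the markers, the minimum is to write down the direction of improvement, the analysis day and the handling of leukopenia and neutropenia, or to label the result descriptive. That is weaker, because the total count would still mix the two effects.
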